#### **Missing day only**

- If the month and year of the incomplete start date are the same as the month and year of the XEN implant date, the day of the XEN implant date will be assigned to the missing day
- If either the year of the incomplete start date is before the year of the XEN implant or if both years are the same, but the month of the incomplete start date is before the month of the XEN implant date, the last day of the month will be assigned to the missing day.
- If either the year of the incomplete start date is after the year of the date of the XEN implant or if both years are the same, but the month of the incomplete start date is after the month of the XEN implant date, the first day of the month will be assigned to the missing day

### **16.6.2 Incomplete Stop Date**

The following rules will be applied to impute the missing numeric fields for an incomplete prior or concomitant medication stop date. If the imputed stop date is before the start date (imputed or non-imputed start date), the imputed stop date will be set equal to the start date.

#### **Missing month and day**

- If the year of the incomplete stop date is the same as the year of the XEN implant date, the month and day of the XEN implant will be assigned to the missing fields.
- If the year of the incomplete stop date is before the year of XEN implant date, *December 31* will be assigned to the missing fields.
- If the year of the incomplete stop date is after the year of the XEN implant date, *January 1* will be assigned to the missing fields.

**Missing month only**

- If only the month is missing, the day will be treated as missing and both the month and the day will be replaced according to the rules described above.

**Missing day only**

- If the month and year of the incomplete stop date are the same as the month and year of the XEN implant date, the day of the XEN implant will be assigned to the missing day.
- If either the year of the incomplete stop date is before the year of the date of XEN implant or if both years are the same, but the month of the incomplete stop date is before the month of the date of the XEN implant, the last day of the month will be assigned to the missing day
- If either the year of the incomplete stop date is after the year of the date of the XEN implant or if both years are the same, but the month of the incomplete stop date is after the month of the date of the XEN implant, the first day of the month will be assigned to the missing day

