## **10.1 PRIMARY EFFECTIVENESS ASSESSMENTS**

### **10.1.1 Primary Analysis**

The primary effectiveness analysis will estimate the proportion of patients, with corresponding 2-sided 95% CI, that achieve at least a 20% reduction from baseline Hour 0 IOP while on the same number or fewer IOP-lowering medications at Month 12 compared with baseline using a mixed-effects repeated measures logistic regression model. The model will include visit as a fixed effect and baseline IOP as a covariate for repeated measures at Month 1, 3, 6, 8, 10, and 12. An unstructured covariance matrix will be used for repeated measures on the same patient; if the model with unstructured covariance fails to converge, an alternative covariance structure will be chosen. The Hour 0 IOP percent change from baseline at a timepoint is calculated as:

$$100 \times (\text{Timepoint Hour 0 IOP} - \text{Baseline Hour 0 IOP}) / \text{Baseline Hour 0 IOP}$$

First, a response variable will be derived from the effectiveness variables: Hour 0 IOP percent change from baseline and the number of concomitant IOP-lowering medications. If the percent change in Hour 0 IOP from baseline is less than or equal to  $-20\%$  at an analysis timepoint of interest **and** the number of IOP-lowering medications taken at the that timepoint is same or fewer compared to that at baseline, the response variable will be coded to value 1 and 0 otherwise. Refer to Section 8.4.2 for a discussion on determining the number of IOP-lowering medications taken at a timepoint of interest. GENMOD procedure available in SAS software will be used to fit the repeated measures logistic regression model; see sample SAS code below:

```
proc genmod data=one(where=(visit gt 0)) descending;
  class visit pid;
  model resp=bliop visit/link=logit dist=bin;
  repeated subject=pid/type=un within=visit;
  lsmeans visit/cl alpha=0.05;
  ods output lsmeans=lsms(keep=visit estimate lower upper);
run;
```

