### **16.0 DATA HANDLING CONVENTIONS**

#### **16.1 VISIT TIME WINDOWS**

Table 16.1–1 presents the analysis visits assigned for efficacy and safety analyses and the corresponding range in Study days (window) during which an actual visit may occur.

Table 16.1–1. Visit Time Windows

Analysis Visit	Target Visit Daya	Window
Baseline	Day 1	Days $\leq 1$
Day 2	Day 2	Days [2, 4]
Day 8	Day 8	Days [5, 11]
Week 2	Day 15	Days [12, 22]
Month 1	Day 31	Days [23, 61]
Month 3	Day 92	Days [62, 137]

Month 6	Day 183	Days [138, 213]
Month 8	Day 244	Days [214, 274]
Month 10	Day 305	Days [275, 335]
Month 12	Day 366	Days $\geq$ 336

a Relative to the date of the XEN implant. Day 1 = the date of the XEN implant. There is no Day 0 or Week 0.

If an assessment date (if the assessment date is unavailable, use visit date instead) is on or after the date of XEN implant, the study day is calculated using (Assessment date – date of the XEN implant + 1). If the assessment date is before the date of the XEN implant, the study day is calculated using (Assessment date – date of XEN implant). Therefore, a negative day indicates a day prior to XEN implant date.

For multiple scheduled or unscheduled visits falling within the same analysis visit window, the assessment closest to the target visit day will be used for by visit summaries. If two visits are equally close to the target visit day, the later visit will be used as analysis visit.

For by visit and severity summaries, the results with maximum severity for the visit should be chosen if multiple scheduled or unscheduled visits falling within the same analysis visit window.

For number of IOP-lowering medications taken during post-baseline visits, analysis visits for IOP measurements will be derived first. Post-baseline analysis visit days of IOP measurements will then be compared to start and stop date of each concomitant IOP-lowering medication record to determine number of IOP-lowering medications taken during post-baseline visits.

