#### **16.6 MISSING DATE INFORMATION FOR PRIOR OR CONCOMITANT MEDICATIONS**

For prior or concomitant medications, including medications of interest, incomplete (i.e., partly missing) start dates and/or stop dates will be imputed. Per database design, year part of a medication start or stop date cannot be set to 'unknown'. When the start date and the stop date are both incomplete for a patient, the start date will be imputed first.

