##### **Missing month and day**

- If the year of the incomplete start date is the same as the year of the XEN implant date, the month and day of the XEN implant will be assigned to the missing fields

- If the year of the incomplete start date is before the year of the XEN implant date, *December 31* will be assigned to the missing fields
- If the year of the incomplete start date is after the year of the XEN implant, *January 1* will be assigned to the missing fields.

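### For IOP-lowering drugs with a known start on or after implantation, SAP 16.6.2 sets every incomplete stop to the earliest possible date, so it can lower but never raise Month 1 to 10 medication counts

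*SAP*

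**What the plan says.** SAP 10.1.1 codes a response when Hour 0 IOP has fallen by at least 20% and "the number of IOP-lowering medications taken at the that timepoint is same or fewer compared to that at baseline". The follow-up count is a date match (SAP 16.1): "Post-baseline analysis visit days of IOP measurements will then be compared to start and stop date of each concomitant IOP-lowering medication record".

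Those dates may be imputed. SAP 16.6 opens: "For prior or concomitant medications, including medications of interest, incomplete (i.e., partly missing) start dates and/or stop dates will be imputed". SAP 8.4.1 identifies the medications of interest as those on the two IOP-medication eCRF pages, so the rule reaches the drugs counted in the endpoint. Only the year is guaranteed to be recorded.

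SAP 16.6.2 then treats an incomplete stop date as follows.
- Month and day missing: "If the year of the incomplete stop date is the same as the year of the XEN implant date, the month and day" of implantation are used. A later year gets 1 January.
- Month only missing: the recorded day is discarded and the rule above applies.
- Day only missing: in the implant month, the implant day is used. In the same year, when "the month of the incomplete stop date is after the month of the date of the XEN implant, the first day of the month" is used. A later year is treated the same way.
- If the result precedes the start date, "the imputed stop date will be set equal to the start date".

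SAP 16.6.1 handles starts in parallel. With the month unknown, "If the year of the incomplete start date is the same as the year of the XEN implant date, the month and day" of implantation are used. With only the day unknown, when "the month of the incomplete start date is after the month of the XEN implant date, the first day of the month" is used.

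Protocol 4.4.1.1 suspends IOP-lowering drugs on Day 1 and allows them to be introduced afterwards, so records that start after implantation are expected.

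**The concern.** The direction of the stop rule favours the medication criterion. A drug truly in use at a visit can drop out of the count, and a patient who needed an extra drug can then score as needing no more than at baseline. Month 1 to 10 responses enter the primary repeated-measures model and are tabulated with confidence intervals (SAP 10.1.1). The by-visit medication counts and change categories are a secondary result (SAP 10.2), and SAP 17.0 drops sensitivity analyses for secondary endpoints.

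The study is single-arm with no hypothesis test, so these estimates are the result. Elsewhere the SAP imputes adversely: for events on or after implantation, missing AE severity becomes severe (16.3) and missing causality becomes related (16.4).

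**Working it through.** The plan gives no figure on incomplete dates, so there is none to reproduce.

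**Step 1: which branches can apply.** A drug started on or after implantation cannot stop before it. The last-day-of-month and 31 December branches of 16.6.2 need a stop before the implant month or year, so they drop out. What remains is the implant date, the first of the month, or 1 January. Therefore:

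imputed stop = later of (start date, first day on or after implantation of the recorded month or year) ≤ true stop.

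Where only the month is missing, discarding the recorded day can move the date earlier than the record allows. The direction is the same.

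**Step 2: worked example** (illustrative dates). Implant 10 Mar 2019, one drug at baseline. Drug A is restarted on 20 Mar and continues. Drug B runs from 1 May to 20 Nov 2019. The SAP 16.1 target days for Months 3, 6 and 8 are Days 92, 183 and 244, that is 10 Mar plus 91, 182 and 243 days: 9 Jun, 8 Sep and 8 Nov. The true count is 2 at all three.
- B's stop recorded as Nov 2019: imputed 1 Nov. The count at Month 8 falls to 1.
- B's stop recorded as 2019: imputed 10 Mar, reset to 1 May. B lasts one day, the count is 1 at all three visits, and a 20% IOP fall now scores as response.

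**Step 3: size per record.** Assumptions: implant dates spread over 2019 (every fifth day); starts evenly spread over Days 2 to 335 (every third day); true stop evenly spread from the next day to Day 365; visits on Days 31, 92, 183, 244 and 305; stop day counted as on drug. This gives 1,606,584 cases with a mean true coverage of 1.436 visits.

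| Unknown part | Visits lost | Visits gained | Net |
|---|---|---|---|
| Stop day, start known | 0.172 | 0 | -0.172 |
| Stop month, start known | 1.103 | 0 | -1.103 |
| Day of both dates | 0.174 | 0.209 | +0.035 |
| Month of both dates | 1.116 | 0.490 | -0.626 |

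With the start known, no imputed stop fell after the true stop. With the stop month unknown, 72% of drugs truly in use at one or more of the five visits vanish from all five. The loss depends on start day. From a Day 8 start to a Day 250 start it runs from 1.81 to 0.49 visits (month unknown) and from 0.21 to 0.13 (day unknown).

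**Step 4: Month 12.** Patients exit at the Month 12 visit (Protocol 6.1.5), and an ongoing drug has no stop to impute. The stop rule alters the Month 12 count only when an incomplete stop falls on or after that assessment.

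**Step 5: weight of one changed response.** 1/65 = 1.5 percentage points with all implanted patients, 1/50 = 2.0 points with 50 evaluable.

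**The case against.** The strongest reply is that the stop rule is half of a pair. SAP 16.6.1 moves post-implant starts to their earliest date, which raises counts. A reader might infer from 16.6.2 that date imputation as a whole biases counts downward. The documents do not support that: when only the days of both dates are unknown, the two rules nearly cancel (+0.035). They do not cancel when the stop alone is incomplete, and that part of the point stands.

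A reader might also infer that the primary Month 12 proportion is inflated. Step 4 shows almost no direct effect. Visit is categorical in the model, so Months 1 to 10 reach the Month 12 estimate only indirectly, and no change in it has been shown.

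The large figures need an unknown stop month. Medications are recorded at every visit (Protocol Table 1-1), regimen changes go on the eCRF (4.4.1.1) and data are source-verified (7.4), so an unknown day is the likelier case. This is fair, although SAP 16.6 does provide for unknown months.

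A lower count is also not a changed response. That needs a true count above baseline, a dropped drug that brings it back to baseline or below, and an IOP fall of at least 20%. Protocol 2.1 cites mean use falling from 3.5 to 1.7 drugs and from 3.3 to 0.9 in earlier XEN experience, so many patients may sit well below baseline. This limits the effect on responses but not on the medication summaries.

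Finally, SAP 16.1 spells out the date match only for post-baseline visits, and a reader might call the baseline count undefined. Protocol 8.2.1 compares with the number before implantation, so that is a wording matter and no part of this point.

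**Conclusion.** The point holds for IOP-lowering drugs with a known start on or after implantation and an incomplete stop. For these the direction follows from the text and rests on no assumption: Month 1 to 10 counts can be lowered and never raised. The size per record, about 0.17 visits with the day unknown and 1.10 with the month unknown, rests on the even spread of dates in step 3 and is not a forecast. The total effect is unknown, because the documents give no frequency of incomplete dates and no estimate of how many responses would change. The Month 12 estimate is barely affected. It is worth correcting because it is cheap and the error favours the device in tabulated results.

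**What to change.** In SAP 16.6.2, for an IOP-lowering drug with a complete start date on or after implantation and an incomplete stop, impute the latest date compatible with the recorded parts. It should never fall before the start, and no later than the day before the Month 12 (or exit) IOP assessment unless the record shows use at that visit.

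The cap matters. Under the step 3 assumptions every drug had stopped before Month 12. A cap at the exit date itself would wrongly count about 11% (day unknown) or 72% (month unknown) as in use there if the stop day counts as on drug. A cap one day earlier gives 0%.

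Keep the current rules where only the days of both dates are unknown, because latest-date stops would turn the net +0.035 into about +0.38. Keep them also for pre-operative drugs, where the implant-date rule matches the protocol's suspension on Day 1.

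Query every record with an unknown start or stop month before database lock. If unresolved, show results under both the earliest and the latest stop. List every patient-visit whose response depends on an imputed date.

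The cost is SAP wording, derivation code, site queries and one listing. Month 1 to 10 counts would be overcounted instead, by about 0.16 to 0.18 visits per record with an unknown stop day (depending on the spacing of the date grid) and about 0.9 with an unknown stop month. That is the conservative direction, and some Month 1 to 10 responders may become non-responders.

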**17.0            CHANGES TO ANALYSES SPECIFIED IN PROTOCOL**

Sensitivity analyses for secondary effectiveness endpoints will not be conducted.

**19.0**            **AMENDMENTS**

**19.1**            **AMENDMENT 1**

1. In Section 10.1.1, clarification added about CRF source for Hour 0 IOP for Baseline and Month 12/Exit visits.
2. In Section 10.1.2, clarification added for SAS code for sensitivity analysis.
3. In Section 10.1.3, added subgroup analysis for Baseline IOP  $\geq 20$  mm Hg and  $\leq 35$  mm.
4. In Section 10.3, clarification added for diurnal IOP analysis.
5. In Section 11.3, clarification added for BCVA analysis.
6. In Section 16.1, added analysis window for Month 8.
7. In Section 16.2, specified that IOP for safety will not be used for efficacy analysis.

**Signature:** [Redacted]  
**Email:** [Redacted]

**Signature:** [Redacted]  
**Email:** [Redacted]

**Signature:** [Redacted]  
**Email:** [Redacted]

**Signature:** [Redacted]  
**Email:** [Redacted]

**Signature:** [Redacted]  
**Email:** [Redacted]

**Signature:** [Redacted]  
**Email:** [Redacted]
